3.2 Safety and biological activity endpoints

Biological activity will be assessed as follows:

Primary endpoint:

Levels (AUC and maximum concentration) of IL-4, IL-5 and IL-13 in nasal filter paper (measured using Luminex) after nasal allergen challenge.

Secondary endpoints:

Total eosinophil counts in nasal lavage fluid, PGD₂ concentrations in filter paper after nasal allergen challenge.

Total nasal symptom scores after nasal allergen challenge.

Adverse events, vital signs, concomitant medication and laboratory safety parameters.

Plasma drug concentrations will be related to IL4, 5 and 13, PGD₂ and eosinophil levels in nasal secretions.

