Cytospin preparation: After calculation of total cell count, the lavage cell suspension is adjusted to 200,000 leukocytes/ml. One cytospin block is prepared, using labelled coated slides. 100 μ l aliquots are loaded onto the blocks. If the dilution factor calculated is less than or equal to two then the sample should not be diluted and all of the residual 200 μ l cell suspension should be loaded onto a single block and one slide should be produced. The cytospin slides are produced by spinning at 450 rpm, medium acceleration, for 3 minutes. Each slide must be labelled as follows:

Subject Initials

Subject Identification Number

Specimen Identification Number

Centre number

Visit number

Sampling time-point

Staining: The four slides are left to air-dry for 30 min, and then fixed in methanol. One slide is stored at room temperature. The remaining slides are stained with Diff-Quik stain, mounted using size 0 cover slip and DPX, and stored at room temperature.

Expression of lavage results: Differential cell counts are determined by assessment of 400 leukocytes on the cytospin. This is converted to a percentage of eosinophils and the total number of eosinophils calculated.

B. Nasal Filter Paper for Assay of Inflammatory Mediators

Materials

1. Filter paper (Whatman No. 42; Whatman Paper Ltd, Maidstone, UK)
2. Dulbecco's phosphate buffered saline (PBS), without magnesium chloride and calcium chloride (Sigma, Product No. D-8537)
3. Bowl and ice packs for sample storage during collection
4. 50 ml polypropylene centrifuge tube (Falcon tube)
5. Tissues and towel
6. Bowl for waste

Filter Paper Procedure

Preliminary discarded nasal wash (see above) to remove mucus.

- a. Two filter strips are cut with scissors to size 7 x 30mm/strip (Whatman No. 42; Whatman Paper Ltd, Maidstone, UK). The sharp corners are trimmed. Pairs of strips are weighed before adsorption of nasal secretions.
- b. An Eppendorf containing Luminex assay buffer (500 μ l) is weighed.

- c. With the Subject sitting comfortably upright, and the head extended backwards, the filter papers are placed together back-to-back on the lateral wall of the **RIGHT** nasal cavity using blunt-ended forceps. Strips are left to absorb nasal secretions for 2 min.
- d. The 2 strips are removed together with blunt-ended forceps, folded in half and placed into the pre-weighed Eppendorf containing Luminex assay buffer (500 μ L). The tube is **reweighed** after the addition of the filter papers.

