- e. The papers are completely submerged in assay buffer and then mixed using a vortex for 15 seconds and then the rolling mixer for 10 minutes to allow mediators to elute.
- f. After centrifugation at 4°C for 10 minutes at 400g (1500rpm), the eluate is collected in fractions of 100 μ l and stored at -80°C.
- g. Luminex analysis. After thawing, a BSA solution (20%) to give a final 2% solution is added to the eluate.
- h. The mixture is then centrifuged through a 0.22 μ m pore size cellulose acetate filters (Costar spin-X ®) at 4°C for 30 minutes at 3200rpm to remove residual mucus.
- i. The mixture is then assessed on the Luminex 100 IS® analyser. Results are generally expressed in terms of pg/ml or pM, relating usually to the 500 μ l of assay buffer eluate. Results can be expressed in terms of the volume of adsorbed secretion.

Filter Paper Processing

1. After removing and reweighing, the two strips are placed together into an assay buffer (500 μ l of PBS pH 7.4, 1%BSA, 0.05% Tween® -20, 0.05% sodium azide).
2. The papers are mixed using a vortex for 15 seconds and then the rolling mixer for 10 minutes to allow mediators to elute.
3. After centrifugation at 4°C for 10 minutes at 400g (1500rpm), the eluate is collected and stored at -70°C for later analysis using Luminex 100 IS® analyser.
4. The eluate is centrifuged through a 0.22 μ m pore size cellulose acetate filters (Costar spin-X ®) at 4°C for 30 min at 3200rpm to remove residual mucus before analysis
5. Results are generally expressed in terms of pg/ml or pM, relating usually to the 500 μ l of assay buffer eluate. Results can be expressed in terms of the volume of adsorbed secretion.

C. Total nasal symptom scores

Nasal symptoms will be scored in terms of nasal obstruction, rhinorrhea, nasal itch and sneezing. All symptoms are scored on a four point scale and the total score for each time point will be assessed. An example score sheet is presented in Appendix 2.

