8.2 Statistical analysis

The primary objective of the study is to assess the effects of OC000459 on levels of IL-4, IL-5 and IL-13 (Th2 cytokines) in nasal filter paper after nasal allergen challenge (NAC). The primary analyses of these effects will be based on the area under the curve of these levels from 1 to 9 hours after NAC (AUC(1-9)) and the maximum level from 1 to 9 hours after NAC (Max(1-9)). These measures of response will be analysed using a two-way crossover analysis with treatment and period as factors and investigating OC000459 versus placebo differences. In addition the IL-4, IL-5 and IL-13 response profiles for OC000459 and placebo will be summarised and compared at each time-point pre-NAC and over the 9 hour period after NAC.

Similar approaches will be used for the analysis and summary of the secondary measures, including Th2 cytokines at 15 and 30 min after NAC, eosinophil counts in nasal lavage fluid, PGD2 levels in nasal filter paper, and total nasal symptoms scores.

After all data have been collected, the top copy of each CRF page will be sent to the data entry and analysis unit of Arros Limited. The bottom copy of the CRF pages will be retained by the investigator.

The relationship between plasma concentrations of OC000459 and the above measures of effect will also be summarised.

In addition, further exploratory analyses will be carried out to fully assess the effects of OC000459.

A randomised code will be prepared by an independent consultant statistician. Subject disposition, demographic and baseline data will be summarised by sequence group and overall. Adverse events, concomitant medication, vital signs and laboratory safety findings will be summarised by treatment group. All safety data will be listed.

Further detail of the statistical analyses and data presentations to be used in reporting the study will be provided in a Statistical Analysis Plan which will be finalised prior to breaking the blind.

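### Does leaving the unit of the filter-paper cytokine result open let a drier nose pass for the 25% reduction the trial is sized for?

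*Protocol*

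**What the plan says.** Section 3.2 defines the primary endpoint as "Levels (AUC and maximum concentration) of IL-4, IL-5 and IL-13 in nasal filter paper" after challenge. Section 8.2 adds the time window: "The primary analyses of these effects will be based on the area under the curve of these levels from 1 to 9 hours" after challenge, together with the maximum over the same window. The model has treatment and period as factors. Neither section names a unit.

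Units appear only in the laboratory method, section 5.5.2.1 part B, once at the end of steps a-i and again at step 5 of the processing list. Results are "Results are generally expressed in terms of pg/ml or pM, relating usually to the" 500 µl of eluate, and "Results can be expressed in terms of the volume of adsorbed secretion".

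Contact time is fixed: "Strips are left to absorb nasal secretions for 2 min". The amount absorbed is not fixed, but it can be derived from weights. Step a says "Pairs of strips are weighed before adsorption of nasal secretions", and the buffer tube is weighed before and after the strips go in.

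The same part describes the handling of the sample twice. Steps a-i reweigh the tube, store at -80°C and include this at step g: "After thawing, a BSA solution (20%) to give a final 2% solution is added to the eluate". The shorter list begins "After removing and reweighing, the two strips are placed together into an assay buffer", mentions no later BSA addition and stores at -70°C.

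**The concern.** With contact time and buffer volume fixed, the eluate level depends on two things: how concentrated the cytokine is in the secretion, and how much secretion the paper takes up. Rhinorrhoea is one item of the symptom score, a secondary endpoint, so the trial itself treats secretion as something that may respond to treatment. If the drug reduced secretion without touching cytokine concentration, eluate pg/ml would still fall. A crossover would not remove that, because the change would follow the treatment. On this reading the primary result could be positive for the wrong reason, and having two permitted units would leave room to choose the more favourable one. Two differing recipes for one sample add a further doubt about what the reported number is.

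**Working it through.** **1. The plan's own figure.** Section 8.1 gives a standard deviation of within-subject differences of 13.4% of the mean, doubled for planning: 2 × 13.4% = 26.8%. With 16 subjects the standard error is 26.8%/√16 = 6.7%. For a 25% reduction at a two-sided 5% level (sidedness is not stated), the noncentral t gives power of 93.6% with 15 degrees of freedom, or 93.4% with 14 when period is fitted. The smallest number reaching 90% is 15, so 16 subjects with more than 90% power is reproduced. The smallest observed difference that would be significant is 2.145 × 6.7% = 14.4%.

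**2. Constant concentration, less fluid.** Let C be the concentration in secretion and v the absorbed volume in µl. The eluate level is E = C·v/(500 + v). The protocol gives no v, so a range of 25 to 200 µl is assumed. Setting the new level to 0.75 of the old, for v = 50: 50/550 = 0.0909; 0.75 × 0.0909 = 0.0682; v' = 500 × 0.0682/(1 − 0.0682) = 36.6.

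| v (µl) | v' giving a 25% lower E (µl) | fall in volume |
|---|---|---|
| 25 | 18.5 | 26% |
| 50 | 36.6 | 27% |
| 100 | 71.4 | 29% |
| 200 | 136.4 | 32% |

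A pure 20% fall in volume lowers E by 18.5% at v = 50. With 16 subjects and a standard deviation of 26.8%, that reaches significance with probability 0.73 (0.56 to 0.77 for v between 200 and 20 µl).

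**3. Constant mass, less fluid.** Now suppose the strip collects the same cytokine mass M in less fluid. Then E = M/(500 + v), and the volume-corrected value E·(500 + v)/v equals M/v. Going from 50 to 36.6 µl, E changes by 550/536.6 = 1.025, a rise of 2.5%. The corrected value changes by 50/36.6 = 1.37, a rise of 37%. In this case the eluate unit is nearly stable and the corrected unit is the misleading one.

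**4. Which case applies.** The documents do not say. Section 1 notes that filter paper probably carries an intracellular signal as well, from adhering cells that lyse. That part need not scale with fluid volume, so the near-proportionality in step 2 is not assured.

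**5. Chance differences in volume.** Sequences are randomised and balanced (section 5.2). If the drug has no effect of any kind, volume varies as noise around zero difference, and a 25% mean shift would be 25/6.7 = 3.7 standard errors. The error rate under no drug effect is not inflated. A false reading needs the drug itself to change secretion.

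**6. BSA dilution.** If the buffer already holds 1% BSA, as the shorter list states, the added fraction x solves 20x + 1(1 − x) = 2, so x = 1/19 = 5.3%. With no BSA in the buffer, 20x = 2 gives 10%. Applied to every sample, this multiplies both treatments by the same factor, and neither the percentage reduction nor the t statistic moves.

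**The case for a change.** The case for a change is that the protocol speaks of cytokines in nasal fluids and secretions (sections 3.1 and 3.2) and favours filter paper because its samples are less diluted (section 1). That points to concentration in secretion as the quantity of interest. The weights are already taken, so naming that unit would cost one calculation per sample. Section 10.9 asks for every item to be followed exactly, which two differing recipes do not allow.

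Part of this stands. The two units can diverge if treatment changes the absorbed volume, one of them has to be settled before unblinding, and the weights make it possible to look at absorbed volume by treatment. The recipes do disagree on what is reweighed, on the BSA addition and on the storage temperature.

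It does not show that the protocol is wrong. The unit wording describes usual laboratory practice and does not fix eluate pg/ml as the endpoint. The endpoint is worded as levels in nasal filter paper, which an eluate value fits. The scale of the 13.4% pilot figure is not stated, so imposing the corrected unit could separate the endpoint from the data it was sized on. The second list reads as a shortened repeat of the first, and its silence on BSA does not forbid that step. Nothing suggests that recipes would be mixed by treatment, and the documents give no figure for an effect of -70°C against -80°C.

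**Conclusion.** The concern does not call for a change. The arithmetic holds: a volume 26% to 32% smaller reproduces the 25% design effect on the eluate scale. It rests on an assumed volume of 25 to 200 µl, constant cytokine concentration, unsaturated paper and a systematic fall in volume on active drug. The documents support none of these. If the drug did reduce secretion, that would be a real drug effect, and the question would be one of mechanism and interpretation. Making the volume-corrected unit primary would exchange one possible bias for another, as the 37% rise in the constant-mass case shows.

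What remains is a unit left unnamed and a duplicated bench description. Section 8.2 leaves further analysis detail to a statistical analysis plan finalised before the blind is broken. That plan is the normal place for the scale of an assay variable, and its timing guards against choosing the unit on the results. It was not available here, so whether it names the unit is not known. The recipe differences are clerical: at most a 5% to 10% common dilution, which cancels provided one recipe is used throughout.

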5.5.3 Assessments for safety

5.5.3.1 Clinical

Heart rate, lying and standing systolic and diastolic blood pressure, body temperature and respiratory rate will be measured in singlicate (once) using well calibrated electronic machines for all measures except respiratory rate. Spontaneously reported adverse events and concomitant medications will be recorded throughout the study. Twelve lead ECGs will be obtained at the screening visit, at day 1 of Treatment Period 2 (Visit 5) and at the final follow up visit.

5.5.3.2 Laboratory

A urine screen for drugs of abuse, an alcohol breathalyser test and a smokerlyzer test will also be obtained at screening and at each subsequent attendance in the unit during the treatment periods.

Laboratory safety assessments at screening, on days 1 and 5 (a.m. and evening) of each treatment period of the study and at follow up will consist of haematology measurements (haemoglobin, haematocrit, MCV, MCHC, total and differential white cell count, platelet count) and clinical chemistry measurements (urea, sodium, potassium, chloride, bicarbonate, creatinine, total bilirubin, AST, ALT, ALP, serum proteins, uric acid, calcium, phosphate, glucose).

Non-compliance and any reasons for it are to be documented in the CRF.
Urine dipstick measurements will be made for protein, blood, ketones and urobilinogen and will be performed on the Clinical Studies Unit.

5.5.4. Drug in plasma blood sampling

All blood samples must be drawn within \pm 5 minutes of the time stipulated in the protocol. The times of blood sampling, centrifugation and placing in the freezer should be recorded in a laboratory notebook. The analytical laboratory for the pharmacokinetic blood samples will be BioDynamics, [name].

Blood samples (2x1 ml) will be taken into 2 ml plastic (Vacutainer) tubes containing lithium heparin and pre-cooled on water/ice (+4°C). Blood samples will be kept on water/ice and will be centrifuged at about 2500xg for 10 minutes at 4°C, within 15-30 minutes of collection (15 minutes is preferred). The resulting plasma will be transferred to two polypropylene vials and immediately frozen. The vials will be kept frozen at -20°C until transferred to BioDynamics for assay. Only one of these aliquots will be shipped to BioDynamics initially for determination of OC000459 by a validated LC-MS/MS assay. The other must be retained on site, stored at -20°C until required. Each sample tube will be clearly labelled with indelible ink with the following information: Plasma. Study number (OC000459/005/05), subject number, time point and dose period and a unique nine-digit code. The actual sampling time after dosing will also be provided at the time of shipment.

Once the collection is complete, samples will be transported deep-frozen (-80°C) and packed in sufficient dry ice to ensure samples arrive frozen at BioDynamics. The shipment documentation should identify whether this is the first or the second set of samples. The outside of the package must clearly indicate that the samples must be placed in a -20°C deep freezer immediately on arrival at the destination.

The packages should be addressed to:

[name]
BioDynamics,
[name],

[name], UK.
[contact]
[contact]
Email: [contact]

Prior to shipment, [name] will be informed of the intended shipment date and date of arrival of the samples at BioDynamics by email or facsimile.

5.6 Compliance checks

Source data will be verified with 100% checks being run on compliance with entry criteria, informed consent documents, CRF signatures, evaluability status, adverse events, withdrawals, out of range laboratory values, 12-lead ECGs, safety blood parameters, biological activity variables and compliance with the medication. A 30% check will be conducted for vital signs, test article blood sampling times and concomitant medications.

In order to be evaluable, volunteers must have given written informed consent, complied with all the entry criteria and the dosing regimen and have completed 90% of all protocol driven measurements. The subjects may be replaced.

Non compliance and the reasons for it are to be documented in the CRF.

5.7 Stopping rules

The trial may be stopped if serious and unexpected adverse events occur which are believed to be OC000459 related. Individual subjects may also be withdrawn from the trial in the event of unacceptable toxicity or non-compliance such that it would affect the interpretation of the data (see section 4.2.3).

6. STUDY MATERIALS

6.1 Study medications

The Investigator and the Royal Brompton Hospital Pharmacy are responsible for investigational product accountability. To this end, all clinical trial supplies will be delivered to and be the responsibility of a suitably qualified and authorised pharmacist, who will document drug disposition and accountability for the duration of the trial. The pharmacist will also perform tablet counts on returned study medications to assess compliance.

6.2 Packaging and labelling

The study medication will be packaged and labelled for each subject by Penn Pharmaceutical Services [[name] [contact]] according to Annex 13, Rev 1 (manufacture of investigational medicinal products) of the EC guide to Good Manufacturing Practice. Supplies will be packed in such a way that the subjects, investigator/study staff, sponsor staff and their representatives are blind to their contents.

6.3 Storage and disposition of study medications

Clinical trial supplies must be stored at 15-25°C in the pharmacy. They must be stored in such a way that they cannot be mixed up or confused with other medications, be they clinical trial supplies or medicines for routine clinical use.

At the end of the trial, the clinical trial monitor will review the drug-dispensing log and reconcile it with the remaining stock of study medication. Eight weeks after completion of the study, any left over study medication will be returned to Penn Pharmaceutical Services for destruction.

6.4 Precautions/overdose

OC000459 is an investigational agent and is contraindicated for all conditions other than those mentioned in this protocol and the Investigator Brochure.

Should an overdose occur, there is no known antidote. Symptoms and signs attributed to the overdose should be treated symptomatically.

OC000459 has been shown in preclinical studies to cause small elevations in fed blood glucose and prolongation of the QRS complex in a single animal. These abnormalities have not been observed in studies OC000459/001/04 and OC000459/003/05 or in longer term 28 day rat and dog toxicology studies. The clinical significance of these findings is unclear.

6.5 Other study supplies.

Case record forms (CRFs) will be supplied by Akos Limited. Each page of the CRF will be supplied in duplicate NCR sheets. The investigator must keep all CRF supplies, both completed and blank, in a secure place.

7. ADVERSE EVENTS

7.1 Definitions

An adverse event is any untoward medical occurrence in a subject administered a pharmaceutical product that does not necessarily have to have a causal relationship with the treatment. All adverse events must be described in the appropriate section of the CRF and their severity and putative relationship to the study medication noted. Definitions of severity are as follows:

Mild: does not interfere with the conduct of the study, resolves spontaneously, does not need medication or any other therapy.

Moderate: requires treatment, interferes temporarily with the conduct of the study.

Severe: forces withdrawal from the study

Serious: death, life threatening, requires or prolongs hospitalisation, results in persistent or significant disability/incapacity, overdose, or is a congenital anomaly/birth defect

Definitions of relationship to study medication are as follows:

Unrelated: bears no relation to timing of medication and similar to symptoms or signs expected in the disease process and does not recur on rechallenge.

Possibly: bears relation to timing of medication and similar to symptoms or signs expected in the disease process and does not recur on rechallenge.

Probably: bears clear relation to timing of medication and distinct from symptoms or signs expected in the disease process and does not recur on rechallenge

Definitely: bears clear relation to timing of medication and distinct from symptoms or signs expected in the disease process and recurs on rechallenge.

Adverse events may also be expected or unexpected. If expected, they will be mentioned in the Investigator Brochure

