5.2 Allocation of treatments and randomisation procedures

Randomisation codes will be generated and will be lodged with the pharmacy department of the Royal Brompton Hospital as well as with the Clinical Studies Unit (see section 8.5 for a full explanation).

The randomisation will be blocked to provide a balanced allocation of subjects to the two sequence groups:

- A. OC000459 in the first study treatment period (Treatment Period 1) and placebo in the second study treatment period (Treatment Period 2)
- B. Placebo in the first study treatment period (Treatment Period 1) and OC000459 in the second study treatment period (Treatment Period 2).

Of the 20 subjects in the study, 10 will be in sequence group A and 10 will be in sequence group B.

Subjects successfully completing the screening assessments and selection procedures will be randomised into the study and will receive the study medication supplies corresponding to the next free number on the randomisation schedule.

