7.2 Serious and unexpected adverse events

All serious adverse events must be reported promptly to the Sponsor and in any case not later than 24 hours after their occurrence. The report must be made by telephone or fax to the following contact at the following numbers:

[name]

Akos Limited

[contact]

[contact]

The Investigator must also complete a serious adverse event form and transfer it to Akos Limited as soon as is possible.

Akos Limited will report all serious, related and unexpected adverse events to the MHRA within 7 days of being notified by the investigator.

7.3 Withdrawals due to adverse events.

Any study subject may be withdrawn from the study at any time at the discretion of the investigator or the request of the subject (see section 4.2.3). The reason for doing so must be clearly documented in the CRF and, if the withdrawal is due to an adverse event, the pertinent page of the CRF must be completed. The Investigator should use his best efforts to follow up the subject following withdrawal from the trial and the appropriate follow up portion of the CRF should be completed at that time.

In general, subjects withdrawn early from the study will be replaced. If withdrawal is caused by an adverse event, which the Investigator considers may be related to the study compound, the subject will not be replaced without reference to the ethics committee responsible for the study.

In the event of any abnormalities considered to be clinically significant by the investigating physician, subjects will be followed up with appropriate medical management until values are considered to be clinically acceptable. Referral or collaborative care will be organised if considered necessary.

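### The causality categories in section 7.1 rely on a rechallenge the crossover does not contain, leave two kinds of event without a category, and are not mapped to the term related in section 7.2

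*Protocol*

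**What the plan says.** Protocol section 7.1 makes the rating compulsory: "All adverse events must be described in the appropriate section of the CRF and their severity and putative relationship to the study medication noted". It then gives four definitions.

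- *Unrelated*: the event "bears no relation to timing of medication and similar to symptoms or signs expected in the disease process and does not recur on rechallenge".
- *Possibly* differs only in its first condition: the event must have a relation to the timing of dosing. The other two conditions stay the same.
- *Probably* asks for a clear time link, an event unlike the disease, and again a negative rechallenge.
- *Definitely* shares the first two conditions of *Probably* but needs a positive rechallenge: the event must be "distinct from symptoms or signs expected in the disease process and recurs on rechallenge".

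There is no residual category and none for an event that cannot be assessed or for a rechallenge that was not done.

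Sections 5.2 and 5.3 fix the exposure. Sequence A takes OC000459 in Treatment Period 1 and placebo in Treatment Period 2, and sequence B the reverse. Each period consists of five single daily doses. No step stops OC000459 and then gives it again.

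Relatedness is used in section 7.2: "Akos Limited will report all serious, related and unexpected adverse events to the MHRA within 7 days", counted from the investigator's notification. Section 5.7 allows the trial to be stopped if "serious and unexpected adverse events occur which are believed to be OC000459 related". Section 8.6 allows early termination for suspected unexpected serious adverse reactions.

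**The concern.** A causality scale should give every event exactly one category from information that the trial collects. This scale asks for the result of a rechallenge that the design does not include. It also makes resemblance to the disease a condition of *Unrelated*, so an incidental injury during washout, plainly unconnected with the capsules, does not meet the definition. An event unlike rhinitis with a loose time link to dosing has no category either, and that is a pattern a drug reaction could show.

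What is at stake is consistent safety classification and reporting. Two assessors could label the same event differently, because the text forces them to improvise. For a serious and unexpected event, that label feeds the decision to report to the MHRA, and the protocol does not link the four labels to the word it uses there.

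**Working it through.** No sample size or power figure is involved. The check codes the four definitions as logical conditions and looks for combinations that have no category.

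**Inputs, all from section 7.1 unless stated**

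- Timing has three levels: none, some relation, clear relation. *Possibly* asks for a relation; *Probably* and *Definitely* ask for a clear one. A clear relation is taken to satisfy *Possibly* as well.
- Resemblance to the disease has two levels: similar, distinct.
- Rechallenge: three categories require no recurrence and one requires recurrence.
- Exposure (sections 5.2 and 5.3): one active period per subject, so the usual state is that no rechallenge was done.

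**Step 1: literal reading.** With rechallenge not done, there are 3 × 2 = 6 combinations of timing and resemblance. All four definitions require a rechallenge result, so 0 of the 6 have a category.

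**Step 2: lenient reading.** Read a rechallenge not done as no recurrence. The same six combinations become:

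| Timing | Similar to disease | Distinct from disease |
|---|---|---|
| None | Unrelated | no category |
| Some | Possibly | no category |
| Clear | Possibly | Probably |

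Four of the 6 are covered and 6 − 4 = 2 are not. *Definitely* does not appear, because it needs a recurrence.

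**Step 3: what the two gaps are.**

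- No time link, unlike the disease: *Unrelated* fails on the resemblance condition, and the other three fail on timing.
- Some but not clear time link, unlike the disease: *Possibly* fails on resemblance, and *Probably* fails because the link is not clear.

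**Step 4: could something else serve as the rechallenge?** Treatment Period 2 cannot, because it gives the opposite treatment. Recurrence after successive daily doses within a period might be argued to count, but the protocol does not define it so. If it did, *Definitely* would become reachable, but both gaps would remain. Events that resemble the disease and recur would then also lack a category.

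**Step 5: the link to reporting.** Section 7.2 uses the bare word related. Section 7.1 never says whether this means *Possibly* and above, *Probably* and above, or *Definitely* alone. An event in the second gap therefore has neither a category nor a rule that decides whether it is related.

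**Step 6: the allergen challenge.** Section 5.1 places it three hours after the fifth dose in both periods. No definition mentions an alternative cause. If challenge symptoms are recorded as adverse events and judged to be time-linked to dosing, the lenient reading puts them in *Possibly* under either treatment.

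**The case against.** The best defence is that the scale works well enough in practice. Section 7.1 asks for a putative relationship, which is a judgement, and a sensible investigator would take no observed recurrence as meeting the rechallenge clause. Three categories then work, and losing the top one does not prevent an event from being called related. This stands, and it means that the documents do not support the inference that relatedness cannot be assigned at all.

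A reader might also list every combination, including those with recurrence, and report a larger number of empty cells. Most of those need a recurrence on rechallenge that this design does not produce, so they are not practical gaps.

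A reader might further infer that stopping the trial depends on the scale. Section 5.7 says that the trial may be stopped and refers to what is believed. Section 8.6 refers to suspected reactions and then to discussion with the sponsor and the Medical Monitor. Neither cites the 7.1 categories. Section 7.2 also requires every serious event to reach the sponsor within 24 hours of occurrence, whatever its cause, so the gap does not hide a serious event from the sponsor.

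On the challenge symptoms, an investigator may reasonably attribute them to the spray rather than to a capsule taken three hours before. They are also captured on a scheduled symptom score, whereas adverse events are reported spontaneously (section 5.5.3.1). Any *Possibly* labels would arise in both periods of a blinded crossover, and no bias between treatments follows.

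The first gap, with no time link, would not be reported as related on any sensible scale. The second gap and the missing definition of related survive all of these arguments.

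**Conclusion.** The definitions do not fit the design and are not exhaustive. Taken literally, no category can be met without a rechallenge. On the lenient reading, *Definitely* stays out of reach and two of six combinations have no category. The one that matters for safety is an event unlike the disease with some but not clear time link, because MHRA reporting turns on a term that the protocol does not map to its own categories.

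This rests on reading the disease process as allergic rhinitis, which section 7.1 does not state; the same two gaps follow whatever disease is meant. The documents give no event frequencies, so the number of events affected cannot be estimated.

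The consequence is limited to safety classification and reporting in a study of up to 20 subjects. The primary analysis and sample size are untouched. Section 8.2 plans to summarise adverse events by treatment group and does not mention relatedness, so a reader should not infer that the planned safety summaries depend on the scale. The change is worth making because it is cheap and the rule as stated misclassifies events.

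**What to change.** Rewrite the relationship definitions in section 7.1 so that they are exhaustive and mutually exclusive and require no rechallenge. Remove resemblance to the disease as a condition of *Unrelated*. Allow the allergen challenge to be recorded as an alternative cause. State in section 7.2 which categories count as related for reporting to the MHRA; the choice is the sponsor's.

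The sponsor should then reconcile the wording of sections 5.7 and 8.6 with that definition. No stopping threshold is proposed here.

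The cost is a wording change in sections 7.1 and 7.2, made through the amendment procedure in section 10.9, and possibly the matching CRF item (the CRF is not among the documents). Visits, procedures and sample size do not change.
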